Secondary outcomes included detection rate of positive findings, number of lesions per patient (NLPP), gastric examination time, and safety of MCCG. Positive findings defined as any pathology detected by MCCG, including polyp, ulcer, gastric fundus varices, submucosal tumor, and carditis. The diffuse lesions such as superficial, atrophic, and erosive gastritis were defined as negative findings [6]. NLPP was defined as the number of positive findings divided by the total number of patients, the location of NLPP were also recorded. Gastric examination time was determined using digital stopwatch in the ESNavi software. Safety of MCCG, or adverse events, defined as symptoms or signs such as abdominal distention, nausea, or vomiting, were monitored closely during the MCCG procedure. Capsule retention (i.e., a capsule endoscope remaining in the gastrointestinal tract for more than two weeks or a capsule endoscope that requires directed intervention or therapy to aid its expulsion) was monitored and followed up for up to two weeks.

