In order to define the sample size, we carried out an exploratory study enrolling 20 patients in each group. Mean gastric cleanliness score in the position change and conventional groups were 20.1 and 19.4, respectively. This study was a superiority study based on two-sided alpha as 0.05 and the power as 80%, thus 64 patients (32 patients in each group) were required by using NCSS-PASS 11 program (version 11.0.7, NCSS, Kaysville, Utah, USA). Considering a withdrawal rate of 20%, we enrolled 80 patients at least. Statistical analysis was performed using SPSS Statistics software version 18.0. Descriptive statistics were given as means ± standard deviation (SD). Differences in categorical variables between patient groups were compared by using the Chi-square test; differences in means were compared with the independent *t*-test. In GCS comparison and subgroup analysis which lack of normal distribution for quantitative data, we used Mann-Whitney test for comparison of the two groups. A *P*-value of < 0.05 was considered to be statistically significant.

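### Does a two-week follow-up make it impossible to observe capsule retention defined as lasting more than two weeks?

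*Protocol*

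**What the plan says.** The Secondary Outcome Measure section of the Protocol lists safety last among the secondary outcomes: "Secondary outcomes included detection rate of positive findings, number of lesions per patient (NLPP), gastric examination time, and safety of MCCG". Capsule retention is described at the end of that section and can be met in either of two ways:

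- by time: "a capsule endoscope remaining in the gastrointestinal tract for more than two weeks";
- by intervention: "a capsule endoscope that requires directed intervention or therapy to aid its expulsion".

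The same sentence then gives the observation period: retention "was monitored and followed up for up to two weeks".

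Neither the Protocol nor the SAP names a fixed status check on day 14, a method of confirming that the capsule has passed, a contact after two weeks, or a rule for a capsule whose fate is unknown when follow-up closes. The SAP does not mention retention.

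**The concern.** Read quickly, the two halves of the sentence seem to exclude each other. The time criterion is met only after two weeks, and two weeks is the longest that anyone is followed. If an event had to be watched happening, none could be recorded by this route, and only the intervention route would remain. Zero time-based retentions in both arms would then say nothing about safety.

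That would matter. Retention is the only safety item in the section that is followed beyond the examination itself, and the Protocol's description of the system says that the capsule contains a permanent magnet. A zero built into the design would give false reassurance, and patients could leave the study with a capsule still inside and no status on record.

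**Working it through.** The documents give no retention figure to reproduce. The check is one of logic, with a little arithmetic for scale.

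**Inputs**

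- Time criterion: T > 14 days, where T is the time from swallowing to expulsion (Protocol, Secondary Outcome Measure).
- Follow-up: at most 14 days (same sentence).
- Planned enrolment: at least 80 (SAP, sample size text).

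**Step 1: what must be known to classify a patient.** The time criterion is a yes/no statement about T, and T > 14 is true exactly when T ≤ 14 is false. It is settled by one fact: whether the capsule has left by the end of day 14.

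| State of knowledge | What follows about T | Time criterion |
|---|---|---|
| Expulsion seen on or before day 14 | T ≤ 14 | Not met |
| Known not expelled at the end of day 14 | T > 14 | Met |
| Last contact on day t < 14, not expelled | T > t only | Undetermined |

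The second row answers the concern: the event can be recorded at the close of the window. Any window shorter than 14 days would leave unexpelled capsules in the third row, so 14 days is the minimum that works.

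**Step 2: the probability of recording an event.** If p = P(T > 14) and status is known at the end of day 14, then P(recorded as retained by time) = p. The expected count among 80 patients is 80 × p, which is zero only if p is zero. The length of observation after day 14 is indeed 0 days, but the classification does not depend on it.

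**Step 3: who falls in the third row.** This depends on how the maximum is read.

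- If follow-up continues until the capsule passes, with two weeks as the cap, those who stop early are in the first row and everyone else reaches day 14. Only patients lost to follow-up are undetermined, and they would be so with a longer window too.
- If follow-up may stop on any earlier day whatever the capsule's status, some patients could be undetermined.

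The first reading is the natural one for an outcome whose purpose is to see whether the capsule has passed. Nothing in the text says that a patient with the capsule still inside is released, or that an unknown status counts as not retained.

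**Step 4: precision, for scale only.** With no events among n patients, the one-sided 95% upper limit is 1 − 0.05^(1/n). For n = 80 this is 1 − 0.05^(1/80) = 0.0368, or 3.7%. It reflects the size of the trial and would be the same for any follow-up length, so it is no evidence of a mismatch.

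**Step 5: reach within the trial.** The sample size rests on the gastric cleanliness score alone. The SAP states that "64 patients (32 patients in each group) were required" and then allows for 20% withdrawal: 64 / (1 − 0.20) = 80, as stated. Retention does not enter.

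**The case for a change.** The best counter-argument accepts the logic and disputes the practice. Classifying at day 14 requires that status be established at day 14, and the documents do not say that it is. A maximum is not a minimum, so a last contact at day 7 or 10 would comply with the wording. Even at day 14, not having noticed the capsule pass differs from confirmed retention unless a method of confirmation is given. Unknowns could then slide into the not-retained column, and that error always runs towards reassurance.

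The plan itself expects losses: "Considering a withdrawal rate of 20%, we enrolled 80 patients at least". If that rate applied to capsule follow-up, which is an assumption, 80 × 0.20 = 16 patients would have unknown status and 80 − 16 = 64 would be known. With no events among the 64, the upper limit is 1 − 0.05^(1/64) = 0.0457, or 4.6%, against 3.7% for 80.

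What stands is that the text omits the end-of-window check, the means of confirmation and the handling of unconfirmed cases. What does not stand is the step from there to an outcome that cannot be observed. The gap between 3.7% and 4.6% comes from losing patients; it is not produced by a two-week window set against a two-week threshold. Nor do the documents contain any rule that treats unknown as not retained.

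**Conclusion.** The concern does not hold. The definition and the follow-up period share the same boundary, and that boundary is where the outcome is decided. A capsule still present when a complete two-week follow-up ends counts as retained; one that has passed does not. A zero count is therefore not forced by the design.

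This rests on two assumptions: that follow-up runs to expulsion or to two weeks, whichever comes first, and that status is known at that point. The first is the ordinary reading of the sentence. The second is usual practice, but it is not written down.

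What remains is thin reporting detail on one component of one secondary safety outcome. The follow-up wording is common to both arms, and the randomised manoeuvre is over before the capsule is swallowed. No conclusion about gastric cleanliness and no part of the sample size depends on it.

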In order to define the sample size, we carried out an exploratory study enrolling 20 patients in each group. Mean gastric cleanliness score in the position change and conventional groups were 20.1 and 19.4, respectively. This study was a superiority study based on two-sided alpha as 0.05 and the power as 80%, thus 64 patients (32 patients in each group) were required by using NCSS-PASS 11 program (version 11.0.7, NCSS, Kaysville, Utah, USA). Considering a withdrawal rate of 20%, we enrolled 80 patients at least. Statistical analysis was performed using SPSS Statistics software version 18.0. Descriptive statistics were given as means ± standard deviation (SD). Differences in categorical variables between patient groups were compared by using the Chi-square test; differences in means were compared with the independent *t*-test. In GCS comparison and subgroup analysis which lack of normal distribution for quantitative data, we used Mann-Whitney test for comparison of the two groups. A *P*-value of < 0.05 was considered to be statistically significant.

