We conducted a single-blind, randomized controlled trial approved by the institutional review board of Shanghai Changhai Hospital (ClinicalTrials.gov. ID: NCT03514966). From May 7 to May 31 2018, consecutive patients (aged \geq 18 years) with upper abdominal complaints requiring MCCG in Changhai Hospital were included after providing informed consent. Patients with the following [7] were excluded: (1) dysphagia or symptoms of gastric outlet obstruction, suspected or known intestinal stenosis, overt gastrointestinal bleeding, history of upper gastrointestinal surgery or abdominal surgery altering gastrointestinal anatomy, or post abdominal radiation; (2) congestive heart failure, renal insufficiency, under therapeutic anticoagulation, in poor general condition (American Society of Anesthesiologists class III/IV), claustrophobia, metallic parts, a pacemaker or other implanted electromedical devices, or artificial heart valves; (3) pregnancy or suspected pregnancy; (4) exclusion criteria for standard magnetic resonance imaging examination such as the presence of surgical metallic devices, even though its low magnetic field technically would not interfere with such devices; or (5) currently participating in another clinical study [6].

Examination were performed by one qualified capsule endoscopist with an experience of more than 500 cases of MCCG operation. Other two endoscopists ([name], [name]) was blinded to the type of gastric preparation, independently graded the quality by reviewing the images captured by MCCG. When discrepancies arise over the grading results, this will be resolved by consensus discussion between the two endoscopists, with arbitration by a third endoscopist ([name]) and made the final decision.

Study intervention

Magnetically controlled capsule gastroscopy system

The MCCG system used in this study includes an endoscopic capsule, a portable external data recorder, a guidance magnet robot, and a computer workstation with software for real-time viewing and controlling, all provided by Ankon Technologies Co. Ltd (Shanghai, China). The endoscopic capsule has a size of 27 * 11.8 mm, with light-emitting diodes surrounding two metal oxide chip cameras placed at both ends. Images are captured and

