recorded at a rate of 2 frame/s, and information sent wirelessly to the data recorder. The view angle of capsule is 140°, and view distance is 0 to 30 mm. It is powered by two silver oxide batteries for up to 10-12 hours. In addition, a permanent magnet was also contained within the dome of capsule, which is guided by the C-arm type guidance magnet robot with five degrees of freedom—two rotational degrees and three translational degrees. Through simulation on the basis of the magnetic field generated by the magnet guidance system, the magnetic field can be adjusted and reaches a maximum of 200 mT. Using two joysticks, the examiner can control capsule movement to varying the strength of magnetic field by altering the distance of the magnet from the patient and change the polarity of the magnet. The size of lesions could be measured by the ESNavi software [5, 6].

Gastric preparation regimen and MCCG examination protocol

After overnight fasting (> 8h), subjects receiving magnetically controlled capsule gastroscopy at the institution who met the inclusion criteria will be randomly allocated into 1 of 2 groups (1:1): position change or conventional groups. An independent research assistant generated the computerized random number sequence. The sequence was concealed in an opaque envelope until the intervention was obtained from eligible subjects, study nurses telephoned the independent research assistant, and then informed the patient's intervention allocation. Right after ingesting 5 g dimethicone (Zigong Honghe Pharmaceutical Co.,Ltd; Sichuan, China) mixed with 100 ml of water, subjects in the conventional group were allowed to walk freely; while subjects in the position change group were instructed by the study nurses to repeatedly change the body position according to a pre-specified protocol for a period of 15 min: in the order of supine position, left lateral position, with a duration of 1 min for each position. Thirty and forty min after dimethicone administration, subjects in both groups would additionally take 200 ml and 800 ml water, respectively before undergoing MCCG examination (Supplementary Figure S1).

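### Does sizing the trial on a 0.7-point difference from a 20-per-group pilot make the stated 80% power wrong?

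*SAP*

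**What the plan says.** The SAP explains that, to set the sample size, "we carried out an exploratory study enrolling 20 patients in each group". It gives the result as "Mean gastric cleanliness score in the position change and conventional groups were 20.1 and 19.4, respectively". It then says "This study was a superiority study based on two-sided alpha as 0.05 and the power as 80" per cent, "thus 64 patients (32 patients in each group) were required by using NCSS-PASS 11 program", and "Considering a withdrawal rate of 20%, we enrolled 80 patients at least".

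It gives no SD for the gastric cleanliness score (GCS), no confidence interval for the pilot difference, and no difference described as worth detecting. GCS is to be compared by the Mann-Whitney test, with results described as means ± SD.

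The Protocol, under the gastric preparation regimen, says patients "will be randomly allocated into 1 of 2 groups (1:1): position change or conventional groups". Its opening paragraph dates inclusion in the past tense: "From May 7 to May 31 2018, consecutive patients".

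**The concern.** The usual basis for 80% power is a difference that clinicians would not want to miss. Here the basis appears to be whatever a small pilot happened to show. A pilot of 40 patients estimates a difference with wide error, and 80% power holds only if both its difference and its SD are right. If the true effect is smaller, the trial could well miss it. Because the SAP plans P-values but mentions no confidence interval for the GCS difference, a non-significant result might then be taken as evidence of no effect. On this view the trial needs about 50 to 53 evaluable patients per group, or 125 to 133 enrolled, in place of 80.

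**Working it through.** **Inputs.** From the SAP: pilot of 20 per group; means 20.1 and 19.4, difference 0.7; two-sided alpha 0.05; power 80%; 32 per group evaluable; 20% withdrawal; at least 80 enrolled. From the Protocol: 1:1 allocation, so 40 per group. Not in the documents: the SD. It is solved back from the other figures and is therefore an assumption.

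**Step 1: the plan's own figures.** The t-test with 32 per group has 80% power at a standardised difference d = 0.7115, so the implied SD is 0.7/0.7115 = 0.984 (0.999 by the normal approximation). With SD 0.98 the t-test formula returns 32 per group. Withdrawal: 64/(1 − 0.20) = 80. The figures are consistent with one another, although 64 cannot be verified without the SD. With all 40 per group evaluable, power at 0.7 is 88%.

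**Step 2: precision of the pilot**, if its SD was the one used. The standard error is 0.984 × √(2/20) = 0.311. The t statistic is 0.7/0.311 = 2.25 on 38 degrees of freedom, P = 0.030. The 95% CI is 0.07 to 1.33 points, or 0.07 to 1.35 in standardised units.

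**Step 3: ordinary power at smaller true effects** (t-test, SD 0.984).

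| True difference | 32 per group | 40 per group |
|---|---|---|
| 0.7 | 80% | 88% |
| 0.525 (three quarters) | 56% | 65% |
| 0.35 (half) | 29% | 35% |

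**Step 4: averaging over the pilot's error.** With a flat prior and the SD treated as known, assurance = Φ[(d√(n/2) − 1.96)/√(1 + n/20)]. Where conditional power is exactly 80% at n = 32, this becomes Φ(0.8416/√(1 + 32/20)) = Φ(0.522) = 70%, whatever the SD. Using the t-test and letting the SD vary as well gives 69% at 32 and 75% at 40 per group.

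**Step 5: dependence on the prior.** The documents support no particular prior. All of those below are assumptions in standardised units.

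| Prior for d, before the pilot | 32 per group | 40 per group |
|---|---|---|
| Flat | 69% | 75% |
| Normal, mean 0, SD 1.0 | 64% | 70% |
| Normal, mean 0, SD 0.5 | 50% | 56% |
| Normal, mean 0.7, SD 0.3 | 74% | 80% |
| Normal, mean 0.8, SD 0.5 | 75% | 80% |

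**Step 6: what 80% assurance would cost.** It needs 50 per group with the SD known: Φ[(0.7115 × 5 − 1.96)/√3.5] = Φ(0.854) = 80%. It needs 53 with the SD uncertain. Enrolled: 100/0.8 = 125 to 106/0.8 = 132.5, so 45 to 53 more than 80. If the planning difference is right, 53 per group has ordinary power of about Φ(0.7115 × √26.5 − 1.96) = Φ(1.70) = 96%.

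**The case for a change.** The best case for a change is that conditional power is only as good as the difference it is conditioned on. When that difference is one worth detecting, the condition is harmless, because missing something smaller is acceptable. The SAP names no such difference, so its 80% rests on an estimate whose interval nearly reaches zero. The point does not need a prior: power of 56% at three quarters of the pilot effect is enough to make it. Enrolling 80 is no answer, since the SAP assigns that margin to withdrawals.

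Much of this stands. The 80% is conditional, the condition is loosely supported, and the SAP gives no reason for 0.7. Three things limit what follows.

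- The stated 80% and the 69% to 75% answer different questions, so the second does not contradict the first. It also moves with the prior, from 50% to 75% at 32 per group in Step 5.
- The absence of any allowance for pilot error is inferred. The SD entered in the sample-size program is not reported. If it was larger than the pilot's, some caution was built in and the interval in Step 2 is too wide.
- Simulating the Mann-Whitney test on assumed score shapes gives 59% to 78% at 32 per group, but this does not isolate pilot error. The lowest case (left-skewed, unequal SDs) has only about 64% power even when the true difference is exactly 0.7, and about 70% averaged power at 53 per group. Most of its shortfall comes from a distribution the documents do not supply, and the larger enrolment would not cure it.

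**Conclusion.** No change follows. The SAP's power figure is a conventional conditional statement that agrees with its own sample size, and no stated figure is missed. Replacing it with assurance would mean 45 to 53 more patients to meet a different criterion, under a prior the documents do not fix. Statisticians would debate that trade-off, and sizing on a pilot estimate is a defensible, if optimistic, choice.

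Timing points the same way. Both documents describe inclusion as past. Once scores exist, the width of the interval matters more than a revised power figure. At SD 0.984 the 95% half-width for the mean difference, t × SD × √(2/n), is about 0.49 points with 32 per group and 0.44 with 40. Readers can derive it from the planned means, SDs and group sizes. Printing it beside the P-value is ordinary good reporting; it leaves the Mann-Whitney test and the superiority conclusion as they are. Nothing in the SAP says that a non-significant result will be read as no effect.

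What remains is a minor reporting gap: the SD used and the reason for choosing 0.7. This conclusion assumes that 0.7 was the design difference, that the implied SD is about 0.98 to 1.0, and that the pilot patients are separate from the trial's, which the documents do not state.

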After attaching the data recorder, patients were asked to lie down on the examination couch beneath the guidance magnet robot. Then the capsule was swallowed in a supine position with approximately 100 ml of water for investigating the esophagus. The patient remained sat upright to facilitate the esophageal passage if capsule stop in the esophagus more than one minute. The examination was conducted with the patient lying in left lateral, supine, and finally right lateral positions. If difficulties in navigation were encountered, further positional change (including the prone position) was tried. Additional water was needed if distension was insufficient. When the capsule reached the stomach, the investigator lifted the capsule away from the posterior wall, rotated and advanced the capsule to the fundus and cardiac regions, and then to the gastric body, angulus, antrum, and pylorus. The gastric examination time of MCCG was recorded. If lesions were identified during MCCG examination, conventional EGD was performed according to standard practice to obtain biopsy or for therapeutic intervention.

Outcome parameters

Primary Outcome Measure

The primary outcome was gastric cleanliness score (GCS). Six primary anatomical landmarks of the stomach (cardia, fundus, body, angulus, antrum, and pylorus) were recorded for evaluation. A 4-point grading scale was introduced to define the cleanliness as excellent (no adherent mucus and foam: score 4), good (mild mucus and foam but does not obscure vision: score 3), fair (considerable amount of mucus or foam present precluding a completely reliable examination: score 2) and poor (large amount of mucus or foam residue needing water to clear it: score 1) (Supplementary Figure S2) [6, 7]. GCS was the total scores of all six landmarks, ranging from 6 (completely unprepared) to 24 (perfect). GCS of \geq 18 was regarded as acceptable.

Secondary Outcome Measure

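### Is 64 patients too few because it needs a gastric cleanliness score SD of no more than about 1.0?

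*SAP*

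**What the plan says.** The sample-size paragraph of the SAP reports an exploratory study with 20 patients per group: "Mean gastric cleanliness score in the position change and conventional groups were 20.1 and 19.4, respectively". It then sets the design values, "This study was a superiority study based on two-sided alpha as 0.05 and the power as 80"%, and concludes "thus 64 patients (32 patients in each group) were required by using NCSS-PASS 11 program". For losses it adds: "Considering a withdrawal rate of 20%, we enrolled 80 patients at least". No SD, standardised effect or PASS procedure is named. SD appears only as a convention for descriptive reporting, without a value. For the score itself, which is not normally distributed, "we used Mann-Whitney test for comparison of the two groups".

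The Protocol, under Primary Outcome Measure, defines the gastric cleanliness score (GCS) from six landmarks, each graded 1 to 4: "GCS was the total scores of all six landmarks, ranging from 6 (completely unprepared) to 24 (perfect"). Grade 2 is "fair (considerable amount of mucus or foam present precluding a completely reliable examination: score 2"). A total of at least "18 was regarded as acceptable".

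**The concern.** A sample size for comparing two means needs a measure of spread, and here that input is missing. The SD implied by 32 per group is about 1.0 point. The Protocol's scale seems to make so small a value hard to reach. The pilot means average a little over 3 per site, and whole-number grades cannot sit at 3.23 or 3.35 without varying. Sites in one stomach share one preparation, so their grades may be positively correlated, and any fair or poor grade adds spread. The acceptability threshold of 18 is six times grade 3, so the scale itself expects some totals that include a grade of 2 or less.

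If the true SD were well above 1.0, the stated 80% would be too high. At an assumed SD of 1.35, a real 0.7-point benefit would be missed about 47% of the time with 64 evaluable patients, not 20%.

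**Working it through.** **Inputs.** From the SAP: means 20.1 and 19.4 (difference 0.7), two-sided alpha 0.05, power 80%, 32 per group, 20% withdrawal. From the Protocol: six sites, whole-number grades 1 to 4, 1:1 allocation. Every SD and correlation below is an assumption unless it is solved from these figures.

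**1. The plan's own figures.** Enrolment reproduces: 64 / (1 − 0.20) = 80. The 64 cannot be computed forwards, so solve for the SD:

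- Normal approximation: SD = 0.7 / [(1.960 + 0.8416) × √(2/32)] = 0.7 / (2.8016 × 0.25) = 0.999.
- Exact t-test (noncentral t): 0.984 at 32 per group and 0.968 at 31, so 32 is the answer for SDs between these two.
- Mann-Whitney: 0.96 to 0.98 for a normal shape, 1.03 to 1.05 for a logistic shape, 1.21 to 1.22 for a double-exponential shape. The SAP names none of these options.

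**2. The scale check behind the concern.** A whole-number grade with mean m between 3 and 4 has smallest variance (m − 3)(4 − m). Assume equal site means and independent sites:

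- Conventional: 19.4/6 = 3.233; 0.2333 × 0.7667 = 0.1789; × 6 = 1.073; SD 1.04.
- Position change: 20.1/6 = 3.35; 0.35 × 0.65 = 0.2275; × 6 = 1.365; SD 1.17.
- Pooled: √[(1.073 + 1.365)/2] = √1.219 = 1.10.

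A common correlation r multiplies the variance by 1 + 5r. With r = 0.1 the SD is √(1.219 × 1.5) = 1.35.

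**3. Power for 0.7 points (t-test).**

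| SD | Assumption | 64 evaluable | 80 evaluable |
|---|---|---|---|
| 0.98 | implied by the SAP | 80% | 88% |
| 1.10 | equal means, independent, grades 3 and 4 only | 70% | 80% |
| 1.35 | as above, r = 0.1 | 53% | 63% |
| 1.65 | 5% fair grades, r = 0.1 | 39% | 46% |
| 1.91 | 5% fair grades, r = 0.2 | 30% | 37% |

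The last column supposes no withdrawals. At the SAP's own 20%, the 64 column applies.

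**4. Is 1.10 a true floor?** No. The function (m − 3)(4 − m) is concave, so equal site means give the largest of the possible independent-site minima. Four sites always at 3 and two averaging 3.7 also total 19.4, with SD √(2 × 0.7 × 0.3) = 0.65. For a whole-number total with no other restriction, the floors are √(0.4 × 0.6) = 0.49 at 19.4 and √(0.1 × 0.9) = 0.30 at 20.1.

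**5. Does positive correlation rule out 0.98?** No. Keep the pilot means, use only grades 3 and 4, and set every pairwise correlation to +0.1. The variance is S + 0.1 × (T² − S), where S is the sum of the site variances and T the sum of the site SDs.

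- Conventional, four sites at 3.05 and two at 3.6 (total 19.4): S = 4 × 0.0475 + 2 × 0.24 = 0.670; T = 1.852; variance 0.670 + 0.1 × (3.428 − 0.670) = 0.946; SD 0.97.
- Position change, four at 3.1 and two at 3.85 (total 20.1): S = 4 × 0.09 + 2 × 0.1275 = 0.615; T = 1.914; variance 0.615 + 0.1 × (3.664 − 0.615) = 0.920; SD 0.96.
- Pooled: √[(0.946 + 0.920)/2] = 0.966; t-test power with 32 per group 81%.

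**6. Can anything be re-sized?** The Protocol's opening paragraph says that patients were included from May 7 to May 31, 2018, and the SAP writes of enrolment in the past tense. On the documents' account, recruitment is over.

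**The case for a change.** The strongest case for acting is that the reader is given a power claim that nobody outside the sponsor can check, and that the implied SD lies at the low end of what the scale suggests. The patterns that reach it need several sites with nearly the same grade in every patient. Even a pilot SD of exactly 0.984 would be imprecise: with 20 per group (38 degrees of freedom), the 95% interval is 0.984 × √(38/chi-square), or 0.80 to 1.27, and at 1.27 power is 58% with 64 evaluable and 68% with 80. The sponsor must hold the SD it used, so disclosing it would cost a sentence.

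Most of this stands as a comment on reporting. It does not show an error. The Protocol names six anatomically different sites and gives no reason to expect equal means, and neither document gives a site mean, a correlation or a frequency of fair grades. The SDs of 1.10 and above therefore rest on unseen inputs, and across the assumed SDs in the table power with 64 evaluable runs from 30% to 80%. Pilot imprecision affects any trial sized from 20 per group and does not single out this calculation.

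**Conclusion.** The concern identifies a real omission but does not support a change. The 64 is consistent with an SD of about 0.97 to 1.00 (t-test or normal approximation), and such an SD is attainable on this scale with the pilot means. If the sponsor's pilot SD was about 1.0 or less, the figure stands. If it was larger, power is lower than stated: 70% at an SD of 1.10, for example, or 80% if all 80 enrolled patients were evaluable.

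Neither case alters what is done. By the Protocol's dates recruitment has closed, so a corrected number could not lead to more patients. The Mann-Whitney comparison at P < 0.05 keeps its type I error whatever SD was entered in PASS. Once the data are in, a non-significant result is best read from the interval for the difference, which a reader can form from the group means and SDs that the SAP already plans to report. What remains is a missing detail that can be filled from the pilot file. This conclusion rests on the Protocol's inclusion dates and on the absence of any site-level data in the documents; a reported pilot SD well above 1.0 would make the power statement wrong, but the analysis would still hold.

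### The SAP applies the Chi-square test to all categorical comparisons, with no rule for small expected counts and no confidence intervals for safety

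*SAP*

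**What the plan says.** The SAP is one unnumbered paragraph. For categorical data it says "Differences in categorical variables between patient groups were compared by using the Chi-square test", and for all tests that a P-"value of < 0.05 was considered to be statistically significant". Neither document mentions an exact test, a continuity correction, a minimum expected count or a confidence interval. Quantitative data are treated differently: the same paragraph moves to the Mann-Whitney test where normality fails.

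On size, the SAP says "thus 64 patients (32 patients in each group) were required" and "Considering a withdrawal rate of 20%, we enrolled 80 patients at least". The Protocol allocates 1:1.

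The Protocol (Secondary Outcome Measure) lists the detection rate of positive findings and safety among the secondary outcomes. Safety has two parts: "Safety of MCCG, or adverse events, defined as symptoms or signs such as abdominal distention, nausea, or vomiting", observed during the procedure, and "Capsule retention (i.e., a capsule endoscope remaining in the gastrointestinal tract for more than two weeks" or needing intervention to be expelled), followed for up to two weeks. No expected rate is given for either.

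**The concern.** The Chi-square P-value is a large-sample approximation that becomes unreliable when expected counts are small. In a trial with 40 patients per arm, safety events are where small counts are most likely. Three things could follow:

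- A sparse table could be called significant when an exact test would not support it.
- Because the variant of the test is not named, the analyst could hold two or three conflicting P-values for the same table, with nothing in the plan to choose between them.
- If an event occurs in nobody, the planned test gives no result, and the plan offers no other summary of how large a risk the data still allow.

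At stake is the reading of the safety results and of any other sparse categorical comparison, not the comparison of gastric cleanliness scores.

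**Working it through.** **Inputs.** From the SAP: 64 evaluable patients (32 per arm), 20% withdrawal, at least 80 enrolled, threshold P < 0.05. From the Protocol: 1:1 allocation. The event counts below are illustrations; the documents give none.

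**Step 1: reproduce the plan's enrolment.** 64 / (1 − 0.20) = 80, or 40 per arm. This matches. (The 64 itself cannot be checked because no standard deviation is given; nothing below depends on it.)

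**Step 2: when is a table sparse?** With equal arms and *t* events in total, the expected count of events in each arm is *t*/2. This is below 5 whenever *t* < 10, at 32 and at 40 per arm alike.

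**Step 3: 4 of 40 against 0 of 40.** Take a = 4, b = 36, c = 0, d = 40, N = 80. The smallest expected count is 2.

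- Uncorrected Pearson: X² = N(ad − bc)² / [(a+b)(c+d)(a+c)(b+d)] = 80 × 160² / (40 × 40 × 4 × 76) = 2,048,000 / 486,400 = 4.21, P = 0.040.
- Yates: X² = N(|ad − bc| − N/2)² / (same denominator) = 80 × 120² / 486,400 = 2.37, P = 0.124.
- Fisher, two-sided: 2 × C(40,4) / C(80,4) = 2 × 91,390 / 1,581,580 = 0.116.

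**Step 4: neighbouring tables at 40 per arm.**

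| Events | Pearson, uncorrected | Yates | Fisher |
|---|---|---|---|
| 3 v 0 | 0.078 | 0.239 | 0.240 |
| 4 v 0 | 0.040 | 0.124 | 0.116 |
| 5 v 0 | 0.021 | 0.065 | 0.055 |
| 6 v 0 | 0.011 | 0.034 | 0.026 |
| 6 v 1 | 0.048 | 0.113 | 0.108 |
| 7 v 1 | 0.025 | 0.062 | 0.057 |

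Four of the six tables change verdict between uncorrected Pearson and Fisher. None changes between Yates and Fisher. The same four change at 32 per arm (4 v 0: Pearson 0.039, Yates 0.121, Fisher 0.113). Fisher is the most conservative of the usual exact tests: for 4 v 0 of 40, Barnard's test gives 0.071 and Boschloo's 0.058, both still above 0.05.

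**Step 5: is the error rate inflated overall?** Enumerating all tables at 40 per arm under equal event rates gives:

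| True event rate | Pearson, uncorrected | Fisher |
|---|---|---|
| 1% | 0.1% | <0.01% |
| 2% | 0.7% | 0.01% |
| 5% | 4.3% | 0.4% |
| 10% | 5.9% | 1.7% |

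The maximum for Pearson over event rates up to 50% is 5.9% (6.0% at 32 per arm). Conditional on the total number of events, the Pearson false-positive rate for totals of 1 to 9 is 0, 0, 0, 11.6, 5.5, 2.6, 10.8, 5.7 and 2.9%. The excess is concentrated at totals of 4 and 7.

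**Step 6: no events in either arm.** Two expected counts are zero, so X² is 0/0. The chance of this at 40 per arm is (1 − p)^80: 45% at a 1% event rate, 20% at 2%, 1.7% at 5%. Fisher returns P = 1, which adds nothing. An interval is informative: the exact two-sided 95% upper limit for 0 of 40 is 1 − 0.025^(1/40) = 8.8%.

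**The case against.** The best defence is that this is a wording gap in a short SAP, with little practical harm. Several parts of that defence stand.

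- A reader might infer that 4 events against 0 would necessarily be declared significant. The SAP does not say so: that holds only for the uncorrected test, and with the Yates correction none of the tables that change verdict would be significant. What remains is that the SAP does not say which applies.
- A reader might infer that safety comparisons carry an inflated false-positive rate. Step 5 does not support this. Overall size is near nominal or below it, and for truly rare events the uncorrected test is itself conservative. The 11.6% at four events is the Fisher P for 4 v 0 in another form, not separate evidence.
- A reader might extend the point to individual lesion types or individual symptoms. The Protocol defines positive findings in aggregate and states no between-group test by lesion type or by symptom.
- A reader might suppose that equal safety will be claimed from a non-significant result. Neither document says so.
- The undefined statistic at 0 v 0 is not a reason to prefer Fisher, since no test is useful there. It is a reason to report an interval.

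The defence does not remove the gap itself. The SAP states one rule for all categorical variables, and that rule can give P-values on both sides of 0.05 for the same small table.

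**Conclusion.** The point holds as a minor, cheap improvement to the analysis of secondary and safety outcomes. The SAP's rule has no small-count provision, does not name the Chi-square variant and gives no interval for safety. At the planned size, tables such as 4 v 0 or 5 v 0 would be significant or not depending on that unnamed variant (0.040 or 0.124; 0.021 or 0.065), with Fisher at 0.116 and 0.055. A zero-event result would have no planned summary.

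This rests on two assumptions: that some adverse events or retention occur in fewer than 10 patients in total, which is plausible but not stated in the documents, and that arms are of 32 to 40 patients. Forty is a planned minimum; at 50 per arm 4 v 0 still gives 0.041 by uncorrected Pearson and 0.118 by Fisher. The primary outcome, the sample size and the main conclusion are unaffected.

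**What to change.** Replace the sentence on categorical variables with:

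> Categorical variables are compared with the Chi-square test, or with Fisher's exact test when any expected count is below 5. Adverse events and capsule retention are reported as counts per arm with exact 95% confidence intervals.

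It would also help to say whether the Chi-square test is used with or without continuity correction.

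The cost is a short text change. It needs no extra patients or data, and SPSS can compute Fisher's test. There are two limits. Fisher's test is conservative, so a few borderline differences will no longer be called significant. The threshold of 5 also does not remove every disagreement: 8 v 2 of 40 has expected counts of exactly 5, so the Chi-square test still applies, and uncorrected Pearson gives 0.042 against Fisher's 0.087. The benefit is that the choice is fixed in advance and that a zero-event result carries a usable statement.
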